7. SAFETY ANALYSES

Unless otherwise specified, summaries of safety data will be provided for the Safety Analysis Set and will include data collected up to the last dose of study drug plus 30 days.

7.1. Adverse Events and Deaths

7.1.1. Adverse Event Dictionary

Clinical and laboratory adverse events (AEs) will be coded using the current version of Medical Dictionary for Regulatory Activities (MedDRA). System organ class (SOC), high-level group term (HLGT), high-level term (HLT), preferred term (PT), and lower-level term (LLT) will be provided in the AE dataset.

7.1.2. Adverse Event Severity

Adverse events are graded by the investigator as Grade 1, 2, 3, 4, or 5 according to toxicity criteria specified in the protocol. The severity grade of events for which the investigator did not record severity will be categorized as “missing” for tabular summaries and data listings. The missing category will be listed last in the summary presentation.

7.1.3. Relationship of Adverse Events to Study Drug

Related AEs are those for which the investigator selected “Related” on the AE eCRF to the question of “Related to Study Treatment.” Relatedness will always reflect the investigator assessment of causality rather than the Sponsor’s. Events for which the investigator did not record relationship to study drug will be considered related to study drug for summary purposes. However, by-subject data listings will show the relationship as missing.

7.1.4. Serious Adverse Events

Serious adverse events (SAEs) will be identified and captured as SAEs if AEs met the definitions of SAE specified in the study protocol. SAEs captured and stored in the clinical database will be reconciled with the SAEs captured in the Gilead safety database before data finalization.

7.1.5. Treatment-Emergent Adverse Events

7.1.5.1. Definition of Treatment-Emergent Adverse Events

Treatment-emergent adverse events (TEAEs) are defined as 1 or both of the following:

- Any AEs with an onset date on or after the study drug start date (Day 1) and no later than 30 days after permanent discontinuation of study drug
- Any AEs leading to premature discontinuation of study drug

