the United States will be limited to subjects who have failed at least 2 biologic therapies (any TNF $\alpha$  antagonists and vedolizumab). Refer to the IB for further information about nonclinical testicular findings.

Administration of filgotinib produces an increase in embryofetal malformations in pregnant rats and rabbits at exposures similar to, or slightly higher than, exposures associated with a 200 mg once daily dose in CD subjects; the use of highly effective contraception in the subject population is expected to mitigate this risk.

JAK inhibition is expected to increase the risk of infection based on mechanism of action. Across global studies with filgotinib, in general, active treatment arms have increased incidences of infection versus placebo. In the present protocol, treatment interruption and discontinuation considerations surrounding infections are incorporated and sites and investigators will be trained regarding such circumstances. All subjects will be screened for tuberculosis (TB) and subjects with active infections will be excluded. Malignancy has been reported in subjects on filgotinib; in the present trial, subjects will be required to have up to date colorectal cancer screening and surveillance and subjects with recent malignancies will be excluded as outlined in the eligibility criteria. For further details about infections and malignancies, please reference the IB.

The potential benefits of JAK inhibition include improvement in clinical symptoms and mucosal and endoscopic healing. JAK inhibition may be efficacious in the treatment of IBD based on results from FITZROY. A lack of response contingency after Week 10 will enable early access to active drug when clinically indicated. In FITZROY, an increase in mean hemoglobin concentration was observed, without difference between filgotinib and placebo. No clinically significant changes from baseline in mean neutrophil counts or liver function tests were observed at 10 weeks. Filgotinib treated subjects showed an increase in HDL and no significant change in LDL. Lipid and hemoglobin effects represent potential benefits in this population.

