#### **3.4. Duration of Treatment**

Randomized subjects will receive a maximum of 24 weeks of study drug. Subjects who are non-responders based on the results of the Week 10 assessments (see Section 3.6) or who meet disease worsening criteria after Week 10 (see Section 3.7) must be discontinued from blinded treatment (see Section 3.5.2).

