### 7.3.1. Adverse Events

Following initiation of study medication, all AEs, regardless of cause or relationship, until 30 days after last administration of study IMP must be reported to the eCRF database as instructed.

All AEs should be followed up until resolution or until the AE is stable, if possible. Gilead may request that certain AEs be followed beyond the protocol defined follow up period.

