## **8.6. Safety Analysis**

Safety will be evaluated by assessment of clinical laboratory tests, physical examinations, ECG and vital signs measurements at various time points during the study, and by the documentation of AEs. All safety data collected on or after the first dose of study drug administration for the entire study (Day 1) up to 30 days after permanent discontinuation of study drug will be summarized by treatment group according to the study drug received.

All data collected during the course of study will be included in data listings.

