3.2. Subject Grouping

For analyses based on the All Randomized Analysis Set and FAS, subjects will be grouped according to the treatment to which they were randomized. For analyses based on the Safety Analysis Set CCI [REDACTED], subjects will be grouped according to the actual treatment received. The actual treatment received will differ from the randomized treatment only when their actual treatment differs from randomized treatment for the entire treatment duration.

CCI

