Treatment-emergent laboratory abnormalities are defined as values that increase at least 1 toxicity grade from baseline at any postbaseline time point, up to and including the date of last dose of study drug plus 30 days for subjects who permanently discontinued study drug. If the relevant baseline laboratory value is missing, any abnormality of at least Grade 1 observed within the time frame specified above will be considered treatment-emergent.

7.2.2.2. **Treatment-Emergent Marked Laboratory Abnormalities**

Treatment-emergent marked laboratory abnormalities are defined as values that increase at least 3 toxicity grades from baseline at any postbaseline time point, up to and including the date of the last dose of study drug plus 30 days for subjects who permanently discontinued study drug.

If the relevant baseline laboratory value is missing, any Grade 3 or 4 values observed within the timeframe specified above will be considered treatment-emergent marked abnormalities.

7.2.2.3. **Summaries of Laboratory Abnormalities**

Laboratory data that are categorical will be summarized using the number and percentage of subjects in the study with the given response at baseline and each scheduled postbaseline time point.

The following summaries (number and percentage of subjects) for treatment-emergent laboratory abnormalities will be provided by lab test and treatment group; subjects will be categorized according to the most severe postbaseline abnormality grade for a given lab test:

- Graded laboratory abnormalities
- Grade 3 or higher laboratory abnormalities
- Marked laboratory abnormalities

For all summaries of laboratory abnormalities, the denominator is the number of subjects with nonmissing postbaseline values up to 30 days after last dosing date.

A by-subject listing of treatment-emergent Grade 3 or 4 laboratory abnormalities will be provided by subject ID number and time point in chronological order. This listing will include all test results that were collected throughout the study for the lab test of interest, with all applicable severity grades displayed.

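### The visible safety windows run to last blinded dose + 30 days with no cut if early-access active drug starts inside them, so events in that overlap would be credited to the original arm

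*SAP*

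**What the plan says.** **Windows.** SAP 7.1.5.1 accepts a treatment-emergent onset "no later than 30 days after permanent discontinuation of study drug", and also any AE that led to stopping study drug. SAP 7 says that safety summaries "will include data collected up to the last dose of study drug plus 30 days". SAP 7.2.2.1 counts laboratory abnormalities "up to and including the date of last dose of study drug plus 30 days for subjects who permanently discontinued study drug". Protocol 8.6 uses the same limit, with data "up to 30 days after permanent discontinuation of study drug will be summarized by treatment group according to the study drug received", and Protocol 8.6.2 repeats it for TEAEs. None of these rules names another end point.

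**Collection.** Protocol 7.3.1 says that "all AEs, regardless of cause or relationship, until 30 days after last administration of study IMP must be reported to the eCRF database".

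**Grouping.** Under SAP 3.2, actual treatment departs from randomized treatment "only when their actual treatment differs from randomized treatment for the entire treatment duration". A subject who took placebo to Week 10 therefore stays in placebo.

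**Stops and early access.** Protocol 3.4 says that Week 10 non-responders, and subjects whose disease worsens later, "must be discontinued from blinded treatment". Protocol 1.5 adds: "A lack of response contingency after Week 10 will enable early access to active drug when clinically indicated". The visible text does not give the start date, dose or database for that access.

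**The concern.** Read together, the visible rules leave a possible overlap of up to 30 days. A subject stops blinded drug at Week 10, may begin active drug, and is still inside this study's safety window under the original treatment label. An infection or laboratory abnormality that arises on active drug would then appear in the placebo column or, for a subject who moves to a new dose, under the original dose.

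The direction matters. Protocol 1.5 reports that active arms have in general had more infections than placebo. Crediting active-drug events to placebo would pull that contrast toward no difference. The pull is strongest in the arm with most Week 10 stops, which one would expect to be placebo, and that arm has only 20 subjects.

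The plan deals with new treatment for efficacy: SAP Appendix 6 sets efficacy data to missing after new steroids, immunomodulators or biologics. The visible safety sections have no counterpart.

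**Working it through.** **The plan's own figure.** The plan gives no number for this issue. Its only precision figure, the 90% exact CI for 16/40, reproduces as 26.94% to 54.22% (stated: 26.9%, 54.2%) but has no bearing here.

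**Inputs from the documents.** Placebo n = 20 and each filgotinib arm n = 40 (Protocol 8.9). Week 10 is Day 71 and Week 24 is Day 169 (Protocol Appendix 2). The window is last dose + 30 days.

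**Inputs assumed.** The last dose falls on Day 71 for a Week 10 stop and on Day 169 for everyone else. k of the 20 placebo subjects stop at Week 10 and all start active drug the next day. The constant first-event hazard is 0.3 per 100 days on placebo and 0.6 on active drug.

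**Per subject.** A Week 10 stop has a window of 71 + 30 = 101 days, of which up to 30/101 = 29.7% could be on active drug. One misattributed subject is 1/20 = 5.0 points in placebo and 1/40 = 2.5 points in a filgotinib arm.

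**Placebo-arm days.** Total = 101k + 199(20 − k); active days = 30k.
- k = 8: 240/3,196 = 7.5%
- k = 10: 300/3,000 = 10.0%
- k = 12: 360/2,804 = 12.8%

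**Range for k.** Protocol 1.4 gives 41% placebo response in the earlier Phase 2 study, so 59% non-response, and 0.59 × 20 = 11.8. That study defined response as a 100-point fall (Protocol 1.2.3.1). Here a 70-point fall or CDAI < 150 at any visit through Week 10 counts (Protocol 3.6), which is easier to meet. So k = 12 is a ceiling.

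**Placebo TEAE incidence.** Incidence = 1 − exp(−Σ hazard × days), averaged over the 20 subjects.
- Non-switcher, 199 days at 0.003: 1 − exp(−0.597) = 44.95%
- Week 10 stop, no active drug, 101 days: 1 − exp(−0.303) = 26.14%
- Week 10 stop, active drug for 30 days: 1 − exp(−0.213 − 0.180) = 32.50%
- Week 10 stop, window cut at Day 71: 1 − exp(−0.213) = 19.18%

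| k | No active drug in window | As the visible rule counts | Shift | Window cut at Day 71 |
|---|---|---|---|---|
| 8 | 37.4% | 40.0% | +2.5 | 34.6% |
| 12 | 33.7% | 37.5% | +3.8 | 29.5% |

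The shift is (k/20) × (32.50 − 26.14) points, so it scales with k: 4 switchers would give 0.2 × 6.36 = 1.3 points. The last column shows that a bare cut errs the other way on crude percentages, by 37.4 − 34.6 = 2.8 points (k = 8) and 33.7 − 29.5 = 4.2 points (k = 12), because it shortens follow-up.

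**Laboratory values.** The post-treatment visit for a Day 71 stop falls at about Day 101. That lies in the Week 14 analysis window (Days 86 to 113, SAP Table 3-3), so by-visit laboratory and vital-sign summaries are exposed in the same way.

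**The case against.** **Redaction.** The strongest reply is that misattribution is not shown. It requires that active drug starts within 30 days of the last blinded dose, that follow-up in this study continues after that, and that the events enter this study's database. The visible text settles none of these. Text is blacked out after the non-responder and worsening rules (Protocol 3.6, 3.7), in post-study care (3.9), after the post-treatment visit sentence (6.9) and after the grouping rule (SAP 3.2). An exception may sit there. Protocol Table 5-1 also bars any JAK inhibitor and any investigational agent through the end of the study, which Protocol 5.4 glosses as 30 days after the last dose. This stands, and it makes the point conditional. It does not remove it: the window definitions are complete visible sentences, and they carry no exception.

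**Stronger readings.** A reader might infer that events on active drug are counted to placebo. The documents support only that they would be, under the conditions above. A reader might also extend early access to subjects with disease worsening. Protocol 1.5 mentions lack of response only, and only when clinically indicated. It does not say that every non-responder switches, or switches at once.

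**Hidden harm.** One might say that a real rise in infections could be hidden. Safety is descriptive, without formal testing. SAP 7.1.6.1 lists all AEs and SAP 4.2.2.1 lists study drug administration, so a careful reader can compare an event's date with the last blinded dose. That limits the harm, but the summary tables would still be affected.

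**Simple truncation.** Cutting the window alone creates a bias of similar size in the other direction. The arithmetic bears this out, and the remedy has to allow for it.

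**Conclusion.** The concern holds in conditional form. The visible TEAE, general safety and laboratory rules do not say what happens if early-access active drug starts inside the 30 days, and the visible grouping rule would leave such events with the original arm.

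The size is 5 points of placebo incidence per affected placebo subject. It is about 2.5 to 3.8 points in expectation if 8 to 12 of 20 switch at once under the assumed hazards. The number of switchers, the immediate start and both hazards are assumptions with no source in the documents, and 12 is a ceiling. The effect is zero if nobody starts active drug within 30 days, if those events are recorded only elsewhere, or if redacted text already excludes them. Only events in those 30 days are at issue, not all later events on active drug.

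**What to change.** Unless redacted text already does so, amend SAP 7, 7.1.5.1 and 7.2.2.1, and align Protocol 8.6 and 8.6.2:

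1. Derive the date of the first early-access dose.
2. Attribute to the original group only events and laboratory values with onset before that date, or by last blinded dose + 30 days if that comes earlier.
3. List and tabulate later events within the 30 days separately, labelled with the drug then being taken.
4. Keep AEs that led to discontinuation of blinded drug as TEAEs, as now.
5. Because the cut shortens follow-up most in the arm with most stops, report exposure-adjusted incidence beside the crude percentages, or show the uncut 30-day table as a sensitivity display.

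The cost is SAP wording, one derived date and one extra table. The downside is up to 30 fewer attributed follow-up days per switcher. Trial conduct and clinical management do not change.

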7.1.5.2. Incomplete Dates

If the onset date of the AE is incomplete and the AE stop date is not prior to the first dosing date of study drug, then the month and year (or year alone if month is not recorded) of onset determine whether an AE is treatment-emergent. The event is considered treatment-emergent if both of the following 2 criteria are met:

- The AE onset date is the same as or after the month and year (or year) of the first dosing date of study drug, and
- The AE onset date is the same as or before the month and year (or year) of the date corresponding to 30 days after the last dosing date of study drug

An AE with completely missing onset and stop dates, or with the onset date missing and a stop date later than the first dosing date of study drug, will be considered to be treatment emergent. In addition, an AE with the onset date missing and an incomplete stop date with the same or later month and year (or year alone if month is not recorded) as the first dosing date of study drug will be considered treatment emergent.

7.1.6. Summaries of Adverse Events and Deaths

Treatment-emergent AEs will be summarized based on the Safety Analysis Set.

No formal statistical testing is planned.

7.1.6.1. Summaries of AE Incidence

The number and percentage of subjects who reported at least 1 TEAE will be provided and summarized by SOC, HLT, PT, and treatment group. For other AEs described below, summaries will be provided by SOC, PT, and treatment group:

- TEAEs of Grade 3 or higher (by maximum severity)
- TEAEs of Grade 2 or higher (by maximum severity)
- All TE treatment-related AEs
- TE treatment-related AEs of Grade 3 or higher (by maximum severity)
- TE treatment-related AEs of Grade 2 or higher (by maximum severity)
- All TE SAEs
- All TE treatment-related SAEs
- All TEAEs leading to premature discontinuation of study drug

- All TEAEs leading to premature discontinuation of study
- All TE SAEs leading to death (ie, outcome of death)
- All TEAEs leading to temporary dose interruption of study drug

A brief, high-level summary of AEs described above will be provided by treatment group presenting the number and percentage of subjects who reported the above AEs. All deaths observed in the study will be also included in this summary.

Multiple events will be counted only once per subject in each summary. Adverse events will be summarized and listed first in alphabetic order of SOC and HLT within each SOC (if applicable), and then by PT in descending order of total frequency within each SOC. For summaries by severity grade, the most severe grade will be used for those AEs that occurred more than once in an individual subject during the study.

In addition, the following tables will be generated and summarized by PT only, in descending order of total frequency:

- TEAEs
- TEAEs of Grade 3 or higher
- TEAEs of Grade 2 or higher
- TE SAEs
- TE treatment-related AEs
- TE treatment-related SAEs
- TEAEs leading to premature discontinuation of study drug

Data listings will be provided for the following:

- All AEs, indicating whether the event is treatment-emergent
- All AEs of Grade 3 or higher
- All AEs of Grade 2 or higher
- SAEs
- Deaths
- All AEs leading to death (ie, outcome of death)

- AEs leading to premature discontinuation of study drug
- AEs leading to premature discontinuation of study
- AEs leading to dose temporary interruption of study drug

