#### **1.4. Rationale for Dose**

In Phase 2 trials in RA, pooled data with an exposure response analysis demonstrated a dose-dependent increase in efficacy up to 200 mg total daily dose. In the Phase 2 study of CD, subjects treated in the 200 mg arm showed favorable response and remission rates (47% remission over 23% placebo and 59% response over 41% placebo). The remission rate at Week 20 for subjects who failed placebo for the first 10 weeks and commenced 100 mg from Weeks 10 to 20 was slightly lower (32%) though the response rate was comparable (59%), indicating some level of efficacy at the 100 mg dose. These results are consistent with the relationship observed between filgotinib exposures and inhibition of pSTAT1 activation (ex-vivo) following single and multiple filgotinib doses, where maximal inhibition of pSTAT1 activation (~78%) was achieved at or above 200 mg total daily dose and intermediate inhibition (~47%) at 100 mg {[Namour 2015](#)}. pSTAT1 data, in conjunction with considerations around the margin for nonclinical testicular findings, suggests assessing doses above 200 mg is not indicated. The presence of response in CD subjects in the exploratory 10 to 20 week arm of Study GLPG0634-CL-211, and study of multiple doses (ie, 100 mg and 200 mg once daily) in the present study will enable establishment of an appropriate nominal dose and determine the dose with the most favorable risk/benefit profile for SBCD subjects.

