7.1.7. Adverse Events of Interest

Adverse events of interest (AEI) include infections, gastrointestinal perforations, herpes zoster, malignancies (excluding non-melanoma skin cancers), non-melanoma skin cancers, major adverse cardiovascular events (MACE), and thromboembolic events. Summaries of the following treatment-emergent AEIs will be produced to enhance the analysis of safety data.

- Events of infections, presented in the following subcategories:

 AEs of infections, utilizing all AEs in the MedDRA Infections and Infestations SOC

 AEs of serious infections, using all AEs in the MedDRA Infections and Infestations SOC that are classified as SAEs

 AEs of herpes zoster, utilizing a MedDRA search term (MST) list developed by Gilead

 AEs of opportunistic infections (OIs), utilizing a narrow scope Standardised MedDRA Query (SMQ)

- AEs of malignancies, excluding non-melanoma skin cancers, utilizing a MST list developed by Gilead
- AEs of non-melanoma skin cancers, utilizing an MST list developed by Gilead
- AEs of gastrointestinal perforation, utilizing an MST list developed by Gilead
- AEs of MACE, utilizing a positively adjudicated event list, presented in the following subcategories (Section 7.1.7.1):

 Cardiovascular (CV) death

 Non-fatal myocardial infarction (MI)

 Non-fatal stroke

- AEs of arterial systemic thromboembolism (ASTE), utilizing a positively adjudicated event list (Section 7.1.7.1)
- AEs of venous thromboembolism (VTE), utilizing a positively adjudicated event list (Section 7.1.7.1)

The number and percentage of subjects with a reported event will be summarized for each treatment group by PT for each AEI category. Data listings for AEIs will also be provided.

The number and percentage of subjects with positively adjudicated TE MACE, TE ASTE, and TE VTE will be summarized by treatment group using the adjudicated category if applicable.

A by-subject listing for subjects with potential events for adjudication (MACE, ASTE, and VTE) and their respective adjudication results will be provided.

A by-subject listing of thromboembolic history and risk factors will be provided for subjects with potential events for adjudication (MACE, ASTE, and VTE).

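### Full-period adverse event percentages may not be comparable between arms, because Week 10 non-responders leave blinded drug and are observed for about half as long; the plan has no table that compares the arms before that rule acts.

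*SAP*

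**What the plan says.** SAP 7.1.6.1 summarises treatment-emergent events, serious events and events leading to discontinuation as subject counts and percentages: "The number and percentage of subjects who reported at least 1 TEAE will be provided and summarized by SOC, HLT, PT, and treatment group". SAP 7.1.7 does the same for infections and the other events of interest: "The number and percentage of subjects with a reported event will be summarized for each treatment group by PT for each AEI category". SAP 7.1.6 adds: "No formal statistical testing is planned".

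The time these percentages cover is set elsewhere. Protocol 3.4 says that Week 10 non-responders, and subjects who meet the worsening criterion afterwards, "must be discontinued from blinded treatment". Protocol 7.3.1 collects adverse events "until 30 days after last administration of study IMP must be reported to the eCRF database as instructed". SAP 7.1.5.1 counts an event as treatment-emergent by onset date if it starts "no later than 30 days after permanent discontinuation of study drug".

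SAP 4.2.1 derives each subject's duration of exposure and tabulates it by arm, but no adverse event table uses it. The readable text has no exposure-adjusted rate, no time-to-event summary and no table cut at Week 10.

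**The concern.** How long a subject is observed depends on CDAI response, which the sponsor expects treatment to change. Protocol 1.4 reports for the earlier Crohn's trial "47% remission over 23% placebo and 59% response over 41% placebo", and SAP 1.3 assumes remission of 40% on filgotinib and 20% on placebo. If those patterns carry over, more placebo subjects have the short window, and a percentage over the whole period mixes event risk with length of observation.

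Safety and tolerability is a stated objective, and Protocol 1.5 says that active arms have generally had more infections than placebo. Readers will make that comparison, and side-by-side percentages are the only between-arm safety comparison that the readable plan offers.

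**Working it through.** **The plan's own figure.** No adverse event rate or safety precision is stated. The one precision figure, the exact 90% interval for 40% remission in 40 subjects (16/40), reproduces: 26.9% to 54.2%.

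**Observation time.** The window adds 30/7 = 4.29 weeks after the last dose.
- Completer: 24 + 4.29 = 28.29 weeks.
- Stopped at Week 10: 10 + 4.29 = 14.29 weeks, a fraction 14.29/28.29 = 0.505.

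**Share stopped at Week 10 (q).** The documents do not give it. One minus the earlier response rates is 41% on filgotinib (200 mg) and 59% on placebo. That response was a fall of at least 100 points (Protocol 1.2.3.1). Here a subject escapes the rule with a 70-point fall or CDAI below 150 at any visit up to Week 10 (Protocol 3.6), so 41% and 59% are best read as upper values. The pairs 20%/40% and 10%/20% below are assumptions without a source.

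**Mean observation** = (1 − q) × 28.29 + q × 14.29.
- Filgotinib: 0.59 × 28.29 + 0.41 × 14.29 = 22.5 weeks.
- Placebo: 0.41 × 28.29 + 0.59 × 14.29 = 20.0 weeks, about 11% less.

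**Crude percentage when the true hazard is equal and constant.** For full-window risk R, the cumulative hazard is H = −ln(1 − R). The risk in the short window is 1 − exp(−0.505 H). The expected percentage is (1 − q) × R + q × (short-window risk).
- R = 50%: short-window risk 29.5%. Filgotinib 0.59 × 50 + 0.41 × 29.5 = 41.6%; placebo 0.41 × 50 + 0.59 × 29.5 = 37.9%; gap 3.7 points.
- R = 20%: short-window risk 10.7%. 16.2% versus 14.5%; gap 1.7 points.

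Gap in points (filgotinib minus placebo):

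| Stopped, filgotinib vs placebo | Mean weeks | R = 5% | R = 20% | R = 50% | R = 70% |
|---|---|---|---|---|---|
| 41% vs 59% | 22.5 vs 20.0 | 0.4 | 1.7 | 3.7 | 4.4 |
| 20% vs 40% | 25.5 vs 22.7 | 0.5 | 1.9 | 4.1 | 4.9 |
| 10% vs 20% | 26.9 vs 25.5 | 0.2 | 0.9 | 2.0 | 2.4 |
| equal shares | equal | 0 | 0 | 0 | 0 |

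If stopping takes effect at Week 12 instead of Week 10, the 41%/59% gaps fall to 1.4 points (R = 20%) and 3.1 points (R = 50%).

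**Against chance.** One of 20 placebo subjects is 5 points. The 90% half-width for 40 versus 20 subjects, 1.645 × √[R(1 − R)(1/40 + 1/20)], is 9.8, 18.0, 22.5 and 20.6 points for the four risks.

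**If the hazard is front-loaded.** Suppose 75% of H falls before week 14.29, with R = 50% and 41%/59% stopped. Crude percentages are 46.1% and 44.4%, a gap of 1.7 points and a ratio of 1.04. For the exposure-adjusted rate, the weekly hazard is 0.75 × 0.693/14.29 = 0.0364, then 0.25 × 0.693/14 = 0.0124. Mean time to first event or censoring is 11.1 weeks in the short window and 18.8 in the long one. This gives 0.59 × 18.8 + 0.41 × 11.1 = 15.6 weeks on filgotinib and 14.3 on placebo. The rate ratio is (0.461/15.6)/(0.444/14.3) = 0.95, although the true hazards are equal. For R = 20% the crude ratio is 1.05 and the rate ratio 0.94.

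**The case against.** A reader might infer that placebo will be observed for less time and that filgotinib will therefore look less safe than it is. The documents do not support that as a statement of fact, for four reasons.

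- The Week 10 rule applies to every arm, and no non-response rate is given for this trial. Filgotinib subjects can also stop early for infection, thromboembolism or toxicity (Protocol 3.5.2).
- Protocol 1.5 mentions early access to active drug after Week 10, with the details redacted. If that drug starts within 30 days of the last blinded dose, its events could fall in the placebo window and offset or reverse the tilt.
- Filgotinib's own percentage is not inflated. Only its contrast with placebo would be affected, and only if risk continues after about week 14.
- Nothing shows a distortion between 200 mg and 100 mg. SAP 1.3 assumes the same remission rate for both doses.

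It is also fair to say that the imbalance would be visible. Exposure by week (SAP 4.2.1) and reasons for stopping (SAP 4.1) are tabulated by arm, and the trial is descriptive. This stands as far as it goes, but a separate exposure table does not let a reader correct the percentage for any given event.

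The strongest objection concerns the obvious remedy. Person-time rates assume a roughly constant hazard. With front-loaded risk they err the other way and make filgotinib look safer, which is the less cautious error. Stopping is also related to active disease, so person-time is not neutral. Placebo would contribute only about 20 × 20.0/52 = 7.7 patient-years, so one event is about 13 per 100 patient-years. The comparison should therefore not rest on such rates.

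**Conclusion.** The concern holds as a question of comparability. The stopping rule and the 30-day window halve the observation of subjects stopped at Week 10, and the planned percentages ignore this. If placebo has more non-responders, the tilt is probably against filgotinib relative to placebo: about 0.4 to 4 points at 41% versus 59% stopped, and under 5 points in every scenario tried. This assumes equal constant hazards, stopping at Week 10, and no other dropout or later worsening. Equal stopping removes the tilt and front-loaded risk shrinks it.

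The shift is smaller than one placebo subject and far inside sampling error, so it does not undermine the trial. It is systematic, though, and sampling error does not cancel it. The Day 1 to Week 10 comparison is free of it because it closes before the rule acts. That makes this a cheap, worthwhile improvement.

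**What to change.** In SAP 7.1.6.1 and 7.1.7:

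1. Add the same number-and-percentage tables for treatment-emergent events, serious events, infections, serious infections and the other events of interest, restricted to onset from Day 1 to the Week 10 visit (or to last dose plus 30 days, if earlier). State that these are the main like-for-like descriptive comparison between arms.
2. Add exposure-adjusted incidence rates (subjects with a first event per 100 patient-years, censored at last dose plus 30 days) only as a supportive full-period summary. State that they assume a roughly constant hazard and that early stopping is related to disease activity.
3. Keep the crude full-period tables as description.

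The cost is SAP wording and a few tables built from onset and dosing dates already held; trial conduct does not change. The Week 10 tables will contain fewer events, say nothing about later ones, and remain open to dropout before Week 10 for other reasons.
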